6.2.3 Blinding

NA

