9.6 Data Analyses

Objective 1. We will determine the performance characteristics of mHRME for the prediction of anal HSIL in flat mucosa and mucosal lesions using histopathology as the gold standard. Our hypothesis is that the sensitivity (SN) specificity (SP), positive predictive value (PPV) and negative predictive value (NPV), as well as the receiver operating curve for the identification of neoplasia on a per biopsy and per patient basis will be high. We will first compare the HRA-directed biopsy (as the gold standard) to the results of the mHRME HSIL diagnosis. The SN of mHRME diagnosis in detection of HSIL will be estimated with the binomial proportion of study participants who are positive for HSIL on HRA-guided biopsy at two thresholds of histology thresholds which are: 1) AIN 2+ threshold, and 2) AIN3+ threshold. SP will be estimated as the proportion of study participants who are negative for HSIL on HRA-guided biopsy at both thresholds. Positive and negative predictive values will be estimated using the binomial proportion and its 95% CI. In addition, the Cohens kappa statistic, and receiver operator characteristic curves will be generated if patient characteristics such as low CD4 count, cART utilization, or high HIV viral load impact the determination of SN and SP. The lab information will be collected and placed in the source document and entered in Oncore. SN and SP of mHRME-based HSIL diagnosis will be estimated on a per lesion and per patient basis with 95% confidence intervals and compared by McNemar's test. A generalized linear model for logistic regression with multiple correlated outcomes will compare SN and SP of each method on a per biopsy and per patient basis. For Device optimization: No Data Analyses are planned.

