 - a. Record scope in time, HRA start time (page 12)
 - b. Record first abnormal area as Biopsy 1 (page 13)
 - i. Describe lesion, mark location, take anoscopy image
 - ii. Record clinician HRA read, plan (standard of care)
 - c. Go onto second abnormal area as Biopsy 2 (page 14)
 - i. Describe lesion, mark location, take anoscopy image
 - ii. Record clinician HRA read, plan (standard of care)
 - d. Repeat above steps for each abnormal area using extra biopsy pages if necessary
 - e. Record HRA end time. Apply Proflavine, insert HRME. Record HRME start time.
 - f. Proceed to first abnormal area (Biopsy 1)
 - i. Once feed is in focus, freeze HRME
 - ii. Record clinician read and plan based on HRME image
 - iii. Analyze image. Record image number and score.
 - iv. Ask clinician if they are happy with this image or if they would like to take another. Take as many images as needed, using extra biopsy pages if necessary
 - v. Select best image of site (most representative)
 - g. Go onto Biopsy 2.
 - i. Once feed is in focus, freeze HRME
 - ii. Record clinician read and plan based on HRME image
 - iii. Analyze image. Record image number and score.
 - iv. Ask clinician if they are happy with this image or if they would like to take another. Take as many images as needed, using extra biopsy pages if necessary
 - v. Select best image of site (most representative)
 - h. Repeat above steps for each Biopsy using extra biopsy pages if necessary
 - i. Record end HRME time. Remove HRME attachment and insert biopsy forceps. Record biopsy start time.
 - j. Proceed to Biopsy 1, biopsy area. Place sample in labeled specimen container. Record specimen label.
 - k. Repeat for each biopsy.

- 1. Record biopsy end time.
- m. Record scope out time.

Within 2 Days of the Clinic:

20. Within 2 days of the procedure, CRC calls the study participant and complete the Follow Up Symptoms form. Be sure to provide the study participant with CRC and PI phone number (business card/consent form) in case of any adverse events. Any adverse events or serious adverse events reported during the phone call should be reported to PI within 24 hours of being reported. If applicable, the CRC and PI will complete the Serious Adverse Event form. The PI will inform the local and IRB of record if needed within 5 days.

Within 30 Days of the Clinic:

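### The software score is recorded before open-ended mHRME retakes and image selection, and 9.6 does not say which image counts, so the algorithm's SN/SP can be biased

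*Combined protocol and SAP*

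**What the plan says.** The order of events is set in Appendix 1 (MOP), step 19. That MOP is titled for Thomas Street Clinic; the second site's steps are not shown.

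- Steps b to d, every abnormal site, before any mHRME image: "Record clinician HRA read, plan (standard of care".
- Steps f and g, per site, once the picture is in focus and frozen: "Record clinician read and plan based on HRME image", then "Analyze image. Record image number and score".
- Next: "Ask clinician if they are happy with this image or if they would like to take another", with the instruction "Take as many images as needed, using extra biopsy pages if necessary".
- Last: "Select best image of site (most representative". No person is named for this step and no criterion is given.
- Biopsy follows once all imaging is finished.

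The entry under "6.2.3 Blinding" is NA. Sections 10.2 and 10.3.3 do provide for blinded pathology reads. Section 9.1 makes both the physician's and the algorithm's mHRME reading part of the primary outcome, set against the Lugol's-guided HRA diagnosis. Section 9.6 plans McNemar's test and a model that "will compare SN and SP of each method on a per biopsy and per patient basis". It does not define the methods or say which of several images of a site is analysed.

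**The concern.** A retake is harmless if it is triggered only by image quality. Here focus is already secured before the image is frozen, so the question about being happy with the image is wider than a focus check, and it comes after the score. Someone who holds an HRA impression and can see a score that contradicts it has a reason to take another image; someone whose score agrees has none. If the later or preferred image is the one analysed, the algorithm's result is drawn towards the expert's HRA impression.

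Two results are exposed. One is the algorithm's own accuracy, which matters because the opening summary and section 5.1 present the software as help for less-experienced clinicians. The other is the paired comparison with HRA, because score-HRA disagreements are exactly the sites that would be imaged again. A larger sample would not remove either effect.

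Separately, the clinician's mHRME read is made by someone who has just recorded an HRA read, so it is a read of mHRME with knowledge of HRA.

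**Working it through.** **1. The plan's precision figure.** The table in 9.2 gives half-widths at 85%, under independence, of 5.28 points (225 slides) and 4.50 (300 slides). The longer arm of an Agresti-Coull interval, taken at 15% by symmetry, reproduces them. For n = 225: adjusted n = 225 + 1.96² = 228.84; adjusted p = (0.15 × 225 + 1.92)/228.84 = 0.1559; arm = 0.1559 + 1.96 × √(0.1559 × 0.8441/228.84) − 0.15 = 5.29 points. For n = 300 the same steps give 4.51. These are the yardstick below.

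**2. Inputs for an illustration.** The documents give no retake rate, no correlation between repeat images and no HRA accuracy, so the bias itself cannot be computed.

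- From the documents: preliminary SN/SP of 94%/92% (opening summary) and 93%/87% (section 2.1).
- Assumed: HRA SN 90%; HRA SP 30% to 80%; binormal scores with correlation ρ of 0.5 to 0.7 between two images of a site; HRA and mHRME errors independent given histology; one retake at a fraction r = 25% to 100% of score-HRA disagreements; the retake counts.

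**3. Formula.** Let p be single-image SN (or SP) and h the HRA SN (or SP). Let d be the probability that the first image is right and the second wrong, which by symmetry equals the reverse: d = p − Φ₂(z, z; ρ), with z = Φ⁻¹(p). A wrong first image is retaken when HRA is right, which gains h·d. A right first image is retaken when HRA is wrong, which loses (1 − h)·d. Hence

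shift = r · d · (2h − 1).

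**4. Results at r = 100%** (divide by 4 for r = 25%):

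| Quantity | d (ρ = 0.5; 0.7) | 2h − 1 | Shift, points |
|---|---|---|---|
| SN 93% | 0.0504; 0.0401 | +0.8 | +4.0; +3.2 |
| SN 94% | 0.0443; 0.0354 | +0.8 | +3.5; +2.8 |
| SP 87%, HRA SP 30% | 0.0830; 0.0648 | −0.4 | −3.3; −2.6 |
| SP 87%, HRA SP 80% | 0.0830; 0.0648 | +0.6 | +5.0; +3.9 |
| SP 92%, HRA SP 30% | 0.0564; 0.0447 | −0.4 | −2.3; −1.8 |
| SP 92%, HRA SP 80% | 0.0564; 0.0447 | +0.6 | +3.4; +2.7 |

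The smallest SN shift is 2.8/4 = +0.7. The SN range is therefore +0.7 to +4.0 points. SP runs from −3.3 to +5.0 and is zero when HRA SP is 50%.

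**5. Sensitivity to the assumptions.** If repeat images were independent, d = p(1 − p). SN 93% then gives 0.8 × 0.0651 = +5.2 points; SP 87% (d = 0.1131) gives −4.5 to +6.8. A lower starting SN leaves more room: at SN 85%, d is 0.0923 (ρ = 0.5) or 0.0718 (ρ = 0.7), and 0.8 × d gives +7.4 or +5.7. The MOP sets no cap on images, whereas this sketch allows one retake.

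**6. Effect on the paired comparison.** Under the same rule, score-HRA disagreement falls by r·d. Among HSIL sites with SN 93% and HRA SN 90%, it starts at 0.93 × 0.10 + 0.07 × 0.90 = 15.6%. With ρ = 0.5 and r = 100% it falls to 15.6 − 5.0 = 10.6%. McNemar's test works on exactly these pairs.

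**The case against.** **A stronger reading that the documents do not support.** A reader might infer that the clinician sees the score, then picks the image that counts, so SN/SP are biased. Three links are missing. The MOP does not say that the score is shown to the clinician; real-time software assistance (sections 1.2 and 5.1) makes it likely, no more. It does not say who selects the best image, and an HRME operator also takes part in the clinic. No section says that the selected image is the one analysed. The supportable statement is that the procedure can bias the result.

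**Protections that stand.** The clinician's read of each image is recorded before that image's score, so the read of the first image cannot be score-driven; only later re-reads can. Biopsy follows imaging and pathology is blinded, so histology cannot drive selection. Section 10.2 can even be read as giving the optical images a blinded read. None of this guards against retakes prompted by the score or the HRA impression.

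**Intended use.** Sections 1.1 and 9.6 describe mHRME used during or together with HRA. For that use, a clinician read informed by HRA is legitimate and needs only accurate description. The exposed quantity is the algorithm's stand-alone result.

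**Perhaps only the analysis plan needs changing.** If every image number and score is logged as step 19 is written, an analysis of the first frozen image can be specified without touching the MOP. That is a fair fallback for patients already imaged. It is weaker than a quality-gated image, because the only gate before that first score is focus.

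**Size.** Retaking at every disagreement is an extreme. At one in four, the SN shift is 0.7 to 1.0 points.

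**Conclusion.** The concern holds in a limited form and should be acted on. In the MOP shown, retakes and image selection come after the score, without a quality rule or a cap, and 9.6 does not fix the image or read to be analysed. This can bias the algorithm's SN/SP and its comparison with HRA, provided the score is visible when the retake is decided and a later or preferred image is the one used. Neither condition is stated.

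Actual size and direction are unknown. On the stated assumptions SN moves up by 0.7 to 4.0 points and SP by −3.3 to +5.0, its sign depending on whether HRA specificity is above or below 50%. The upper values are comparable with the planned half-widths of 4.5 to 5.3 points; the lower ones are minor. Confidence is medium, and the second site's procedure could not be checked.

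**What to change.** 1. In MOP step 19 at both sites, accept or retake each image on written focus and quality criteria before the score is displayed, then lock it. Further images remain allowed; log each with its score and the reason for taking it.
2. In 9.6, state that the primary algorithm SN/SP uses the score on the first accepted image, with the selected best image as a sensitivity analysis. For patients imaged under the present order, specify the first frozen image if the log permits.
3. In 9.6, describe the clinician's read as mHRME used with knowledge of HRA. Locking the image does not remove carry-over of the HRA impression into that read; this wording only discloses it.

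Score-driven selection of the primary image then disappears by construction, and sample size and precision are unchanged. The cost is a small edit to the MOP, the case report form and the SAP. Apparent accuracy may change slightly: SN probably lower, SP in either direction. No extra reader or patient is needed.

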Appendix 2: Study Calendar

Form	Day 0 (Procedure Day)	Day 2	Day 30	Year 1	Year 2
Procedure Form					
Symptoms	X	X	X		
HRA Assessment	X				
Procedure Time	X				
HRME and Biopsy	X				
Pathology	X				
Medical History Form					
Medical History	X				
Physical Exam	X				
Cyto/Pathology Review	X				
Post Procedure Form					
Post Procedure Questionnaire	X				
Follow Up Evaluation				X	X
